## **16.0 Confidentiality**

*16.1* Data Security:

Absolute confidentiality will be maintained. All data will be stored in locked offices and will not be released outside of the study team without consent of the participant. Data that is collected will be entered into OnCore, REDCap, and Box which are accessible only by the study team. Data to be used in scientific presentations or publications will not contain participant identifiers. As this study is funded by the National Institutes of Health, a Certificate of Confidentiality will be in place to help protect the research data from disclosure to outside entities.

## **17.0 Provisions to Monitor the Data to Ensure the Safety of Participants**

*17.1* Data Integrity Monitoring.

The study will undergo regular monitoring (at least annually) of the facility, staff and study documents by clinical research associates at the University of Minnesota's Clinical Trial Monitoring Service, which specializes in regulatory compliance for clinical trials associated with the Food and Drug Administration. This service provides regular monitoring of all research-related activities and is offered free of charge through the University of Minnesota Clinical and Translational Science Institute (CTSI). Monitoring of fidelity to the protocol (e.g., protocol deviations) will be performed at each monitoring visit. Monitoring staff will present a summary report to the PI after each monitoring session. If necessary, corrective action plans will be devised and implemented by the PI to address deficiencies.

*17.2* Data Safety Monitoring.

Responsible Individual: [name] will be responsible for data and safety monitoring and will review all adverse events and serious adverse events regularly throughout the trial. A data and safety monitoring board (DSMB) has been established and includes one adult endocrinologist, one pediatric endocrinologist and one biostatistician. DSMB members are not to be affiliated with the study. The DSMB will meet regularly (frequency to be determined by the DSMB) during the trial to review data and evaluate participant safety. A charter for the DSMB to outline the responsibilities and procedures for the conduct of the monitoring board has been developed and approved by its members along with a

plan for frequency of data review prior to the commencement of the trial. Review materials for the DSMB will be prepared and presented by the study biostatistician, [name] (co-mentor). A report from each meeting will be sent to the PI and her mentorship team advising on the continuation of the study and any suggestions for trial improvement. This report will also be sent to the assigned NIH Program Director and the University of Minnesota Institutional Review Board (IRB). An important charge of the DSMB will be to closely monitor progress and timelines related to recruitment goals, fidelity to the protocol (e.g. regularly review the number and types of protocol deviations), as well as monitor the quality and integrity of the data. The DSMB will communicate any concerns relevant to these issues of trial conduct to the PI and her mentorship team and note specific recommendations for improvement in the meeting report.

**Overall Framework:** There will be a specific and comprehensive plan for monitoring the safety of participants and the integrity of the study data, which will include careful assessment and appropriate reporting of adverse events and use of a DSMB as described above. Adverse events will be monitored closely, and participants will be provided with information about the risks/side effects of the study medication (PHN/TPM) and study procedures. Participant safety is the study team's utmost priority. Accordingly, [name] will involve a team of experienced clinical investigators who will adhere to the standards of the International Conference on Harmonisation Good Clinical Practice (ICH GCP), applicable U.S. Code of Federal Regulations (CFR), and the protocol, which will be approved by the University of Minnesota IRB. Adverse events and protocol deviations will be reviewed by [name], the clinical nurse, and research coordinator after each study visit. Additionally, [name] will receive guidance and regulatory support from her mentorship team and the Center for Pediatric Obesity Medicine's Regulatory Specialist, [name], CCRC.

**Participant Safety:** At the outset, participant risk will be minimized by study team adherence to exclusion and inclusion criteria during screening. The proposed research will expose the participants to a minor increase over minimal risk. The exclusion criteria include, but are not limited to, contraindications to PHN/TPM. Participant assessments will be done at study visits every three months. Participants and their parent/guardian (if < 18 years) will be provided with contact information for [name] (study PI), clinical nurse, and the research coordinator with explicit instructions to contact the study team in the event of emergencies.

**Participant Stopping Rules:** In the event that a participant has a serious adverse event that is deemed related to the study medication and/or procedures by the PI, the participant will be required to immediately discontinue the intervention. The overall study may be stopped at any time at the request of the PI and/or the DSMB. Participants will be removed from the study if suicidal ideation, excessive

weight loss, or disordered eating is present at any time during the trial or if any clinically significant changes (at the discretion of the PI) in mood and/or depression are observed. If the ratio of participants on medication vs. placebo developing a serious adverse event requiring withdrawal exceeds 4:1 (after  $\geq 50\%$  enrollment and a minimum of 5 total events, regardless of group assignment), the trial will be stopped. Patients will be instructed that they may withdraw from the study at any time and for any reason without impact on their typical clinical care.

**Study Integrity:** As stated above, the study will undergo annual monitoring of the facility, staff, and study documents by clinical research associates of the University of Minnesota Clinical Trials Monitoring Service. Monitoring staff will provide a summary report to [name] and her mentorship team after each site visit. If necessary, corrective action plans will be devised and implemented by [name] to address deficiencies.

The PI and research coordinator will generate administrative reports describing the study progress, subject recruitment, subject demographic data, subject status, compliance with inclusion/exclusion criteria, and adverse events. The study statistician and co-mentor, [name], will review data on adverse events, and notify [name] if any events pose statistical concern or occur in disproportionate numbers throughout the intervention groups. Further, the PI and research coordinator will regularly monitor data for accuracy.

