### *11.2 Withdrawal Procedures:*

Participants who wish to withdraw from the study will be allowed to do so. They will also be offered to stop taking the study medication/placebo but continue with the visits.

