### *11.3 Termination Procedures:*

Participants who withdraw from the study will not have additional study information collected. Data that had been collected prior to their withdraw will still be reviewed and utilized.

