## **12.0 Risks to Participants**

### *12.1 Foreseeable Risks:*

#### *Expected Adverse Events*

PHN/TPM: Adverse events will be reviewed and documented at each study visit and phone call (monitored monthly throughout the study). Participants will be instructed to contact study staff immediately if any adverse event is experienced. Overall, the safety profile of PHN/TPM has been demonstrated to be acceptable in adults, with paresthesia (mild tingling in the extremities), dysgeusia (altered taste), insomnia, constipation, and dry mouth as the most commonly reported (incidence  $\geq 5\%$ ). Of note, topiramate use during the first trimester of pregnancy is associated with an increased risk of oral clefts in the fetus. A basic metabolic panel at weeks 0, 24, and 52, and urine pregnancy test (for persons of child-

bearing potential) will be performed monthly. We will require all sexually active participants who are of child-bearing potential to confirm use of at least two forms of effective contraception. In addition, we will monitor for potential changes in depression, anxiety, suicidal behavior and ideation, acute myopia and secondary angle closure glaucoma, mood and sleep disorders, cognitive impairment, metabolic acidosis, kidney stones, and elevated creatinine. Participants will be asked to increase their fluid intake in order to help decrease the concentration of substances involved in kidney formation. Topiramate can increase the risk of suicidal ideation and behavior. Participants will be screened for depression with the PHQ-9 and suicidal ideation and behavior with the C-SSRS. If any questionnaire reveals suicidal behavior or ideation with some intent to act on it, then test results will be confirmed by the PI prior to discharging the subject from the study. Study medications will be weaned off if there is suicidal behavior or ideation with some intent to act on it.

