#### 12.7 Time Period and Frequency for Event Assessment and Follow-Up

All AEs will be captured on the appropriate case report form (CRF). Information to be collected includes event description, time of onset, clinician's assessment of severity, relationship to study product (assessed only by those with the training and authority to make a diagnosis), and time of resolution/stabilization of the event. All AEs occurring while on study must be documented appropriately regardless of relationship. All AEs will be followed to adequate resolution.

Any medical condition that is present at the time that the participant is screened will be considered as baseline and not reported as an AE. However, if the study participant's condition deteriorates at any time during the study, it will be recorded as an AE.

The study staff will record all reportable events with start dates occurring any time after informed consent is obtained until 7 days (for non-serious AEs) and 30 days (for SAEs) after the last day of study participation. At each in person study visit the study staff will inquire about the occurrence of AEs/SAEs since the last visit. Events will be followed for outcome information until resolution or stabilization.

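### Section 17.2 takes participants out of the study rather than only off study drug, so an early removal can leave the week-24 BMI unmeasured and filled by LOCF; the effect is small and the remedy cheap

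*Combined protocol and SAP*

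**What the plan says.** Section 17.2 (Participant Stopping Rules) uses two different consequences in one paragraph. For a serious adverse event judged related to study medication or procedures, "the participant will be required to immediately discontinue the intervention". For the other triggers the wording is "Participants will be removed from the study if suicidal ideation, excessive" "weight loss, or disordered eating is present at any time during the trial", with clinically significant changes in mood or depression added at the PI's discretion. No threshold is given for excessive weight loss.

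Section 12.1 also treats leaving the study and stopping drug as separate steps. If a questionnaire shows suicidal behavior or ideation with some intent, "then test results will be confirmed by the PI prior to discharging the subject from the study". It then adds: "Study medications will be weaned off if there is suicidal behavior or ideation with some intent to act on it".

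On data after exit, 11.3 says "Participants who withdraw from the study will not have additional study information collected". Section 11.2, speaking of participants who wish to withdraw, says "They will also be offered to stop taking the study medication/placebo but continue with the visits". Section 11.1 allows a discretionary final visit with physical examination and HbA1c, written for those who ask to leave. Section 12.7 records new adverse events "until 7 days (for non-serious AEs) and 30 days (for SAEs) after the last day of study participation" and follows them to resolution or stabilization; it does not provide for BMI.

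Section 14.3 makes ITT at 6 months the primary analysis. Section 14.4 fills a missing final measurement by LOCF in that analysis, adds MCMC multiple imputation as a complementary analysis, and promises to examine missing-data mechanisms beyond measured covariates.

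**The concern.** A participant removed before week 24 under 17.2 would have no measured primary endpoint, and the reason for leaving would not be ignorable. Excessive weight loss is close to the outcome itself and is likelier on PHN/TPM. Mood change may be treatment-related: 12.1 lists mood disorders among the monitored risks, and Table 1 in 2.2 reports moody/irritable in 10.9% of treated patients.

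With 15 per arm, each such value is one fifteenth of an arm. LOCF freezes a weight recorded on drug. If the question is the effect of assignment regardless of stopping, any later regain goes unseen and the difference is overstated. Multiple imputation does not repair this, because it has no off-drug data from these participants. Removals after week 24 do not touch the primary endpoint.

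**Working it through.** **The plan's own figure.** Section 14.2 gives SD 8.9, correlation 0.75 and 15 per arm.
- Adjusted SD = 8.9 × √(1 − 0.75²) = 5.887.
- SE of the difference = 5.887 × √(2/15) = 2.150.
- Detectable difference at 80% power, two-sided 0.05 (sidedness assumed) = (1.960 + 0.842) × 2.150 = 6.02, against the stated 6%.
- With 13.5 per arm, 2.802 × 5.887 × √(2/13.5) = 6.35, against the stated 6.3%.

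The plan's figures reproduce, so 2.150 serves as the yardstick.

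**Does a removed participant lose the week-24 value?** 17.2 distinguishes leaving the study from stopping drug, and so does 12.1. 11.3 speaks of those who withdraw. Extending it to removal by the investigator is an inference, supported by 11.1, which uses 'withdrawn' for PI-initiated exits as well. The off-drug visits in 11.2 are offered only to those who wish to withdraw, and the 11.1 exit visit is discretionary. Nothing guarantees a week-24 BMI.

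**How large is the effect of the weight-loss trigger?** The inputs below are assumptions.
- On-drug difference of −6 at week 24, SD 5.887 in each arm, height held fixed.
- Loss follows either a straight line, f = t/24, or an early plateau, f = (1 − e^(−t/10))/(1 − e^(−2.4)), with visit noise of SD 1 at weeks 4, 8, 12, 16 and 20.
- Removal at the first visit at or beyond the threshold.
- Active-arm regain in proportion to time off drug: 50% at 12 weeks, less before that, capped at 50%. The alternative is 50% whatever the time.

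One million simulated participants per arm; each cell shows linear / plateau. 'Over' is the LOCF overstatement of the treatment-policy difference.

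| Threshold | Active removed of 15 | Chance of at least one | LOCF difference (last weight) | Over, regain scaled to time | Over, 50% regardless |
|---|---|---|---|---|---|
| 20% | 0.02 / 0.09 | 2% / 9% | −6.00 / −6.00 | 0.01 / 0.03 points (under 0.02 SE) | 0.02 / 0.07 points (0.01 / 0.03 SE) |
| 15% | 0.35 / 0.80 | 30% / 56% | −5.93 / −5.92 | 0.07 / 0.27 points (0.03 / 0.12 SE) | 0.19 / 0.43 points (0.09 / 0.20 SE) |
| 12% | 1.2 / 2.1 | 72% / 90% | −5.76 / −5.74 | 0.24 / 0.67 points (0.11 / 0.31 SE) | 0.55 / 0.94 points (0.25 / 0.44 SE) |

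The time scaling matters because removals cluster late. At 12/15/20%, 70/85/97% of linear-path removals and about 28/39/59% of plateau-path removals fall at week 20, leaving four weeks for regain.

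**The other direction.** Against the on-drug effect of −6, LOCF from the last weight pulls the difference toward zero: at 15%, by 6 − 5.93 = 0.07 to 6 − 5.92 = 0.08 points, under 0.05 SE. If only a visit with measured height counts as a BMI (weeks 0 and 12 before week 24), LOCF gives −5.79 / −5.78 at 15%, about 0.1 SE.

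**The remaining triggers.** The documents give no rate for suicidal ideation or disordered eating. Table 1 gives 10.9% with moody/irritable and 1.8% discontinuing for it, but over a mean of 11.1 months of uncontrolled clinic treatment. Those rates cannot be carried unscaled to removal by week 12, and most such reports resolved on treatment (83%). I therefore give no figure for these triggers.

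**The case against.** The strongest reply is that the gap is partly one of wording. 17.2 does not say that visits stop, 11.3 does not mention removal, and an exit examination under 11.1 could produce a late BMI. That is fair as far as it goes: the loss of data is an inference, but nothing secures the value either.

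Second, the harm depends on the estimand. ITT in 14.1 defines who is analysed, not how off-drug data are treated, and 4.1 states the goal as BMI reduction on the maximum tolerated dose. For that on-drug effect an off-drug week-24 weight would not help. This stands, and it is why the estimand should be stated.

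Third, 14.4 already promises multiple imputation and an examination of other mechanisms. These probe sensitivity but cannot supply the missing off-drug value.

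Fourth, a 12% threshold is a weak reading of 'excessive' where 2.2 anticipates an 8-10% mean BMI reduction at 52 weeks. I agree, and do not rest the size on it.

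Fifth, safety cover after exit is not absent: 12.7 follows events to resolution or stabilization, and 5.2 provides mental-health or primary-care referral. Only new-event recording is limited, to 7 and 30 days.

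Sixth, 12.1 ties discharge for suicidality to behavior or intent after PI confirmation, so that trigger may fire less often than 17.2 alone suggests.

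**Conclusion.** The point holds as a minor one. 17.2 ends participation where stopping drug would do, and on the natural reading the week-24 BMI is then unmeasured and filled by LOCF for a reason linked to outcome or treatment.

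At assumed thresholds of 15-20%, the overstatement of a treatment-policy difference is about 0.03-0.12 SE at 15% and under 0.02 SE at 20% with time-scaled regain. It is at most about 0.2 SE if half the loss returns regardless of time. At 12% it would be 0.11-0.31 SE on the time-scaled basis. Threshold, weight path and regain are all assumed.

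A reader might infer that the rule seriously biases the primary result, or that the bias is known to favor PHN/TPM. The documents support neither. The expected number of weight-loss removals is below one at the plausible thresholds, the sign depends on the estimand and on which value is carried, and the direction for the mood, suicidality and eating triggers is unknown. Nor do the documents state outright that removed participants are never measured again.

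**What to change.** Keep every clinical trigger.

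- **17.2:** replace removal from the study with discontinuation of study drug, and align the 12.1 wording on discharge so that the two sections agree.
- **11.2:** extend the offer of off-drug visits to these participants, at least for week-24 and week-52 height, weight and adverse-event assessment. Omit the 500-calorie-deficit counselling of 5.2 for anyone stopped for disordered eating or excessive weight loss.
- **11.3:** limit it to participants who decline further follow-up.
- **14.3:** state that the measured week-24 BMI enters the ITT analysis as a treatment-policy effect, with LOCF used only when no week-24 value exists.

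The cost is a protocol wording change and a few off-drug visits that are already on the schedule; the sample size does not change. The consent forms are not among the documents, so whether they need a matching line cannot be checked. The downside is that a value measured after stopping includes off-drug time and does not estimate the on-drug effect.

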### 4.0 Study Intervention(s)/Investigational Agent(s)

#### 4.1 Description:

##### *Phentermine/topiramate Therapy*

Participants randomized to PHN/TPM will initiate treatment at 3.75 mg/23 mg orally once daily in the morning for 14 days, which will then be increased to 7.5 mg/46 mg orally once daily in the morning for 14 days, which will then be increased to 11.25 mg/69 mg orally once daily in the morning for 14 days, which will then be increased to 15 mg/92 mg orally once daily in the morning for the remainder of the trial. There will not be a pause in dose titration between weeks 4 and 12 as indicated by the medication labeling as this pause is indicated to clinically assess weight loss response on mid-dose PHN/TPM before up-titrating to high-dose PHN/TPM. However, the goal of this proposed study is to assess BMI reduction on the maximum tolerated dose of PHN/TPM in a clinical research setting. Therefore, an assessment of weight loss on the moderate dose of

PHN/TPM between weeks 4 and 12 is not warranted. Participants unable to tolerate the dosing regimen will be maintained at the maximally tolerated dose. Following the final study visit, all participants will be down-titrated gradually by taking medication every other day for seven days before stopping treatment altogether. PHN/TPM will be purchased from an independent vendor by the University of Minnesota Investigational Drug Service Pharmacy (IDS). Placebo will be manufactured by IDS. The placebo capsules manufactured by IDS will not be able to be matched to the commercial product. The PI and research coordinator will not be involved in pill counting to evaluate adherence for this trial in order to preserve the blinding of investigators. Participants will not be told which treatment arm they are in to preserve the blinding of participants. Participants will be instructed to take the medication under the supervision of a parent/guardian and pill counts of returned product will serve as a proxy of treatment adherence. If the average fasting plasma glucose (FPG), measured by CGM, is >185 mg/dL after titration to PHN/TPM 15mg/92mg or maximum tolerated dose, metformin therapy or basal insulin therapy will be started or titrated for a goal average FPG <110 mg/dL.

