#### *Insulin Therapy*

Insulin will be started per the American Diabetes Association guidelines on any participants whose A1c is >8.5%. For those treated with insulin prior to enrollment, basal insulin dose will be reduced by 20% at start of PHN/TPM therapy and then by 20% every 4 weeks if average FPG is <110 mg/dL. Basal insulin dose will continue to be reduced every four weeks until basal insulin dose is below 0.2 units/kg/day and then basal insulin will be stopped. If the FPG value is >185 mg/dL after titration to maximum tolerated dose of PHN/TPM and metformin, basal insulin therapy will be started or titrated up by 20% until for a goal average FPG <110 mg/dL. If participants are on rapid-acting insulin meal dosing (carbohydrate coverage), this will be discontinued at the start of the PHN/TPM therapy and only restarted if two-hour post-prandial plasma glucose >200 mg/dL. Rapid-acting insulin will be used as a rescue medication for BG >200 mg/dL per PI discretion.

4.2 Drug/Device Handling:

The PHN/TPM that will be used for this study will be stored with the IDS pharmacy. Placebo will be manufactured by IDS. The IDS pharmacy specializes in storing and dispensing investigational drugs for clinical trials. Study physicians will write a prescription in order for IDS to dispense the study medication. IDS is a secure facility (behind two locked doors) and maintains refrigerators and freezers with temperature tracking to assure that the drugs utilized in this study will maintain stability. IDS will keep detailed records on the receipt of investigational product (including lot numbers) and detailed records on the dispensing of product to each subject enrolled in the study. IDS is also equipped to destroy any medication that remains at the end of the study or any product that is returned by the study participants. IDS will also hold the randomization key for the study, which was developed by the study biostatistician, and will follow their internal standard operating procedures for breaking the blind in the event of an emergency.

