The PI will notify the IRB of any SAE that meets the definition of being unexpected (in terms of nature, severity or frequency), that is related or possibly related to participation in the research and places the subject or others at increased risk of harm per current IRB policy within five days of knowledge of the event. The PI will be responsible for notifying the FDA of any unexpected fatal or life-threatening suspected SAE as soon as possible, but in no case later than seven calendar days after the PI's initial receipt of the information in compliance with the FDCA (21 U.S.C. §§ 301 et. seq.) as well as the implementing regulations [Title 21 of the Code of Federal Regulations (CFR)]. Non-fatal or non-life-threatening SAEs will be reported to the FDA no later than 15 days after the PI's initial receipt of the information. The PI will report any (1) serious, unexpected suspected adverse reactions, (2) findings from other clinical, animal, or in-vitro studies that suggest significant human risk, and (3) a clinically important increase in the rate of a serious suspected adverse reaction to the FDA no later than 15 calendar days after determining that the information qualifies for reporting [21 CFR 312.32(c)(1)]. The PI will also submit annual progress reports within 60 days of the anniversary of the date that the IND becomes active.

The DSMB will be provided with AE and SAE information prior to their review of the study, at least every six months.

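### Section 17.2 has the statistician report between-group adverse event imbalances directly to a named person, most likely the PI, without routing the notice through the DSMB or limiting it to pooled data

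*Combined protocol and SAP*

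**What the plan says.** The last paragraph of section 17.2 gives the study statistician, who is also a co-mentor, the task of reviewing adverse event data and notifying a named individual "if any events pose statistical concern or occur in disproportionate numbers throughout the intervention groups". The sentence does not mention the DSMB.

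The DSMB has its own channel. Section 12.7 states: "The DSMB will be provided with AE and SAE information prior to their review of the study, at least every six months". Section 17.2 adds: "Review materials for the DSMB will be prepared and presented by the study biostatistician". Neither says whether the material is by arm or pooled.

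On blinding, section 4.1 says of two people, the coordinator and the PI, that they "will not be involved in pill counting to evaluate adherence for this trial in order to preserve the blinding of investigators". Section 8.3 gives the Week 12 pill count to someone outside the study. Section 4.2 has the pharmacy manage the switch to open label so that the team stays blinded. It also says of allocation: "IDS will also hold the randomization key for the study, which was developed by the study biostatistician".

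On discretion, section 4.1 leaves metformin titration to the PI and says: "Rapid-acting insulin will be used as a rescue medication for BG >200 mg/dL per PI discretion". Section 11.1 lets the PI withdraw participants who do not upload CGM data. Section 17.2 has the PI judge whether a serious event is related, which forces discontinuation of the intervention, and lets the PI decide whether mood changes warrant removal.

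**The concern.** Whether events are unevenly distributed between groups is comparative information. Several provisions keep the PI from learning about allocation, and this sentence then opens a route by which between-group information reaches the person who is most likely the PI. No reason is given for that route, although an independent board with its own biostatistician already exists.

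What is at stake is mainly the secondary outcomes and retention. A1c and total daily insulin dose are Aim 2 outcomes (section 14.3), and metformin and rescue insulin decisions bear on both. Withdrawal decisions can also touch the primary analysis, because participants who withdraw contribute no further data (section 11.3) and missing final measurements are filled by last observation carried forward (section 14.4). Section 5.3 expects enrolment and completion to take 36 months, so a notice could arrive while other participants are still in the blinded period or have not yet entered it.

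**Working it through.** The question is mainly who is told what, so the passages are set side by side first.

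1. **Who receives the notice.** Section 17.1 says: "Monitoring staff will present a summary report to the PI after each monitoring session". The Study Integrity paragraph of 17.2 sends that same report to a named woman and her mentorship team. Elsewhere 17.2 refers to the PI and her mentorship team. The Responsible Individual paragraph says that one named person "will be responsible for data and safety monitoring and will review all adverse events and serious adverse events regularly throughout the trial". The removed name is therefore most likely the PI. This is an inference.

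2. **What the notice contains.** It reports disproportion between the intervention groups. The text promises no tables or arm labels, and it does not rule out stating the direction.

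3. **What the statistician can see.** Judging disproportion requires data split by group. Coded groups would be enough, so full unblinding is not implied.

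4. **How much an unlabelled notice might reveal (illustration).** Inputs: Table 2 in section 2.2 gives paresthesia in 31% on active treatment and 7% on placebo, over 56 days, in groups of 13 and 14. Section 14.2 gives 15 per arm. The illustration assumes that these rates apply and that the arms are independent binomials.
   - Expected cases: 15 × 0.31 = 4.65 on active; 15 × 0.07 = 1.05 on placebo.
   - Probability that active exceeds placebo by at least 3 cases: 0.70. Probability of the reverse: 0.001.
   - A notice that paresthesia was uneven would therefore usually show its direction without any labels.

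5. **Whether such a notice would be sent.** The plan sets no threshold. If it were Fisher's exact test at 0.05, a split of 5 against 1 would give p = 0.17, and the rates above would reach significance in the active-excess direction only about 24% of the time. A looser trigger would fire more often.

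6. **Effect of the fix on the design figures.** The plan gives no figure on this point. Its sample size figure reproduces: the baseline-adjusted SD is 8.9 × √(1 − 0.75²) = 5.887, and the detectable difference is (1.960 + 0.842) × 5.887 × √(2/15) = 6.02, against the stated 6%. None of these inputs depends on who receives the notice.

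**The case against.** The strongest reply is that the notice adds little. The placebo capsules cannot be matched (section 4.1), and the PI already sees individual events and knows the earlier paresthesia rates, which are printed in the protocol. From those rates alone, under 1:1 allocation, a participant with paresthesia is on active treatment with probability 0.31/(0.31 + 0.07) = 82%. That stands. The 82% describes ordinary side-effect unblinding, which rerouting the notice would leave unchanged, so it does not measure this defect. What the notice adds is in-trial confirmation and possibly a flag on events nobody suspected.

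A reader might also infer more than the documents support:

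- **That the DSMB is bypassed or replaced.** It is not. Sections 12.7 and 17.2 give it regular adverse event information through the same statistician. Its charter is not in the documents and might govern such notices.
- **That the statistician is stated to be unblinded.** The text says only that the statistician developed the key and the pharmacy holds it.
- **That the PI receives arm-level results.** The text promises a notice of imbalance.
- **That the PI controls all insulin dosing and causality grading.** Basal insulin follows written thresholds and steps (section 4.1), and general causality is graded by the examining clinician (section 12.6). The PI's explicit roles are the narrower ones listed above.

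Restricting the PI also has to fit two other provisions. The by-arm 4:1 stopping rule in 17.2 names no assessor, and section 12.7 makes the PI report to FDA a clinically important rise in the rate of a serious suspected adverse reaction. The fix must cover both.

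**Conclusion.** The point holds as a weakness in the information flow. A written rule sends notice of between-group adverse event imbalance directly to a person who is most likely the PI, with no requirement that it pass through the DSMB or be limited to pooled data. That conflicts with the plan's own blinding measures, because the same person makes discretionary decisions on treatment, withdrawal and serious-event relatedness.

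The added bias cannot be sized from the documents. It is probably small for BMI and more plausible for insulin dose, A1c and dropout. The weak blind limits what the change can protect but is no reason to keep an avoidable leak. The conclusion assumes that the removed name is the PI and that the charter does not already redirect such notices. It does not need the statistician to be fully unblinded. The change is cheap and worth making, but this is not a critical flaw.

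**What to change.** Reword the sentence in section 17.2 so that the statistician sends any between-group adverse event imbalance to the DSMB, through its chair and between meetings if needed. The PI and study team would receive individual events as now, pooled adverse event data, and the DSMB's recommendation.

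Add three short statements:

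- who has access to group-level data, and whether it is coded or unblinded;
- that the DSMB, with the statistician, applies the existing by-arm 4:1 stopping rule;
- that the DSMB releases to the PI whatever is needed to meet the FDA reporting duties in section 12.7.

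The charter should be brought into line. The cost is a few sentences and one extra step before the study team learns of an imbalance. Individual events still reach the PI without delay, and the emergency unblinding route in section 4.2 is unaffected. Sample size, power and type I error do not change.
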